6.7.4. Biological samples evaluation

6.7.4.1. Immunological read-outs

Table 12 Immunological read-outs (Amended 10 December 2017)

Blood sampling timepoint			No. subjects [†]	Component	Components priority rank
Type of contact and timepoint*	Sampling timepoint	System			
Screening (Day -29 to Day 0)	Pre-Vaccination	Whole blood	≤96 [‡]	IL-2, CD40L, 41BB, TNF- α , IFN- γ , IL-13, IL-17 secreting T-cells	1
		Serum	≥ 96	Respiratory Syncytial virus Ab.IgG (RSV F or G antibody)	1
			≥96 [‡]	Anti-RSV A Neutralizing Antibody	2
				Respiratory Syncytial Virus F protein Ab.IgG (Anti-RSV PreF antibody)	3
				Respiratory Syncytial Virus F protein Ab.IgG (Palivizumab competing Ab)	4
Visit 5 (Day 30)	Post-Vaccination 1	Whole blood	≤96 [‡]	IL-2, CD40L, 41BB, TNF- α , IFN- γ , IL-13, IL-17 secreting T-cells	1
		Serum	~96	Anti-RSV A Neutralizing Antibody	1
				Respiratory Syncytial Virus F protein Ab.IgG (Anti-RSV PreF antibody)	2
				Respiratory Syncytial Virus F protein Ab.IgG (Palivizumab competing Ab)	3
Visit 9 (Day 60)	Post-Vaccination 2	Whole blood	≤96 [‡]	IL-2, CD40L, 41BB, TNF- α , IFN- γ , IL-13, IL-17 secreting T-cells	1
		Serum	~96	Anti-RSV A Neutralizing Antibody	1
				Respiratory Syncytial Virus F protein Ab.IgG (Anti-RSV PreF antibody)	2
				Respiratory Syncytial Virus F protein Ab.IgG (Palivizumab competing Ab)	3
Visit 10 (Day 365)	Post-Vaccination 2	Whole blood	≤96 [‡]	IL-2, CD40L, 41BB, TNF- α , IFN- γ , IL-13, IL-17 secreting T-cells	1
		Serum	~96	Anti-RSV A Neutralizing Antibody	1
				Respiratory Syncytial Virus F protein Ab.IgG (Anti-RSV PreF antibody)	2

CD40L: cluster of differentiation 40 ligand; IFN- γ : interferon gamma; IgG: immunoglobulin G; IL (IL-2; IL-13; IL-17): interleukin; TNF- α : tumor necrosis factor alpha; RSV: respiratory syncytial virus.

* Blood samples for CMI taken on Day 7 and Day 37 for subjects enrolled under protocol amendment 1 will still be assessed for CMI.

[†] *The target will be to enroll up to 96 RSV-seropositive infants aged 12 to 23 months at the time of first vaccination (unless the dose escalation IDMC decision can be made based on the evaluation of accumulating safety data on fewer subjects) to ensure that at least 64 infants receive two doses of study vaccine (ChAd155-RSV or Placebo) (see Section 5.1) (Amended 10 December 2017).*

[‡] Only in investigational sites with a laboratory in proximity capable to perform WBS necessary for the CMI assay.

[‡] Blood samples for CMI and for humoral immunogenicity may be postponed until after the RSV serostatus is known and eligibility is confirmed up to or on Day 0 (but before vaccination).

In case of insufficient blood sample volume to perform assays for all antibodies, the samples will be analyzed according to priority ranking provided in [Table 12](#).

Table 13 Molecular biology for nasal swab and specimen analysis (Amended 10 December 2017)

Blood sampling timepoint			No. subjects†	Component	Components priority rank
Type of contact and timepoint	Sampling timepoint	System			
Surveillance for asymptomatic RSV-RTI	Monthly contact during the RSV season	Nasal swab	~96	Quantitative RT-PCR (RSV A RNA and RSV B RNA)	Not applicable
Assessment of potential RSV-RTI	All subjects attending assessment visit	Nasal swab	Event-driven	Quantitative RT-PCR (RSV A RNA and RSV B RNA)	Not applicable
Assessment of potential RSV-RTI	All subjects attending assessment visit with positive Quantitative RSV A/B RT-PCR results	Nasal swab	Event-driven	Qualitative multiplex PCR** (Influenza A virus (Flu A) Influenza B virus (Flu B) Human respiratory syncytial virus A (RSV A) Human respiratory syncytial virus B (RSV B) Human Influenza A virus subtype H1 (Flu A-H1) Human Influenza A virus subtype H3 (Flu A-H3) Human Influenza A virus subtype H1pdm09 (Flu A-H1pdm09) Human adenovirus (AdV) Human metapneumovirus (MPV) Human enterovirus (HEV) Human parainfluenza virus 1 (PIV1) Human parainfluenza virus 2 (PIV2) Human parainfluenza virus 3 (PIV3) Human parainfluenza virus 4 (PIV4) Human bocavirus 1/2/3/4 (HBoV) Human rhinovirus A/B/C (HRV) Human coronavirus 229E (229E) Human coronavirus NL63 (NL63) Human coronavirus OC43 (OC43))	Not applicable
Assessment of potential RSV-RTI	All subjects presenting confirmed LRTI* (with negative Quantitative RSV A and B RT-PCR results)	Nasal swab	Event-driven	Qualitative multiplex PCR** (Influenza A virus (Flu A) Influenza B virus (Flu B) Human respiratory syncytial virus A (RSV A) Human respiratory syncytial virus B (RSV B) Human Influenza A virus subtype H1 (Flu A-H1) Human Influenza A virus subtype H3 (Flu A-H3) Human Influenza A virus subtype H1pdm09 (Flu A-H1pdm09) Human adenovirus (AdV) Human metapneumovirus (MPV) Human enterovirus (HEV) Human parainfluenza virus 1 (PIV1) Human parainfluenza virus 2 (PIV2) Human parainfluenza virus 3 (PIV3) Human parainfluenza virus 4 (PIV4) Human bocavirus 1/2/3/4 (HBoV) Human rhinovirus A/B/C (HRV) Human coronavirus 229E (229E) Human coronavirus NL63 (NL63) Human coronavirus OC43 (OC43))	Not applicable

Blood sampling timepoint			No. subjects [†]	Component	Components priority rank
Type of contact and timepoint	Sampling timepoint	System			
Assessment of potential RSV-RTI	All subjects attending assessment visit	Other specimen	Event-driven	Locally available RSV assay	Not applicable
Assessment of potential RSV-RTI	All subjects attending assessment visit	Other specimen	Event-driven	Locally available RVP assay	Not applicable

PCR: polymerase chain reaction; RSV: respiratory syncytial virus; RTI: respiratory tract infection; RVP: respiratory viral panel.

[†] *The target will be to enroll up to 96 RSV-seropositive infants aged 12 to 23 months at the time of first vaccination (unless the dose escalation IDMC decision can be made based on the evaluation of accumulating safety data on fewer subjects) to ensure that at least 64 infants receive two doses of study vaccine (ChAd155-RSV or Placebo) (see Section 5.1) (Amended 10 December 2017).*

* Refer to Table 4 for the case definitions.

** The list of components might be subject to change in case equivalent kit is used for multiplex RVP testing.

6.7.5. Immunological correlates of protection

No generally accepted immunological correlate of protection has been established so far for the antigens used in the candidate ChAd155-RSV vaccine.

7. STUDY VACCINES AND ADMINISTRATION

7.1. Description of study vaccines

The investigational ChAd155-RSV vaccine has been developed and manufactured by GSK Biologicals.

The Quality Control Standards and Requirements for the candidate vaccine are described in separate Quality Assurance documents (e.g. release protocols, certificate of analysis) and the required approvals have been obtained.

The vaccines are labeled and packed according to applicable regulatory requirements.

Table 14 Study vaccines

Treatment name	Vaccine name	Formulation	Presentation	Volume to be administered	Number of doses
ChAd155 5x10 ⁹ vp	ChAd155-RSV	ChAd155-RSV=1*10 ¹⁰ vp/mL	Liquid in monodose vial	0.5 ml	2
ChAd155 1.5x10 ¹⁰ vp	ChAd155-RSV	ChAd155-RSV=1*10 ¹¹ vp/mL	Liquid in monodose vial	0.15 ml	2
ChAd155 5x10 ¹⁰ vp	ChAd155-RSV	ChAd155-RSV=1*10 ¹¹ vp/mL	Liquid in monodose vial	0.5 ml	2
Placebo 0.5	Formulation buffer S9b	Na ₂ HPO ₄ =1.3mg; KH ₂ PO ₄ =186µg; NaCl=3.85mg; KCl=100µg; MgCl ₂ =50µg *	Clear liquid	0.5 ml	2
Placebo 0.15	Formulation buffer S9b	Na ₂ HPO ₄ =0.4mg; KH ₂ PO ₄ =56µg; NaCl=1,16mg; KCl=30µg; MgCl ₂ =15µg *	Clear liquid	0.15 ml	2

* Same concentration of buffer S9b is used for Placebo 0.5 and Placebo 0.15. Values indicated here are the quantities contained in the volume to be administered.

7.2. Storage and handling of study vaccines

The study vaccine must be stored at the respective label storage temperature conditions in a safe and locked place. Access to the storage space should be limited to authorized study personnel. The storage conditions will be assessed during pre-study activities under the responsibility of the sponsor study contact. The storage temperature should be continuously monitored with calibrated (if not validated) temperature monitoring device(s) and recorded. Refer to the Module on Clinical Trial Supplies in the SPM for more details on storage of the study vaccines.

Temperature excursions must be reported in degree Celsius.

For the placebo any temperature excursion outside the range of 0.0 to +8.0°C (for +2 to +8°C/+36 to +46°F label storage condition) and for the ChAd155-RSV vaccine any temperature excursion above -60°C (for ≤ -60°C/≤ -76°F label storage condition) or below -90°C must be reported in the appropriate (electronic) temperature excursion decision form ([e]TDF). The impacted IMPs must not be used and must be stored in quarantine at label temperature conditions until usage approval has been obtained from the sponsor.

Refer to the Module on Clinical Trial Supplies in the SPM for details and instructions on the temperature excursion reporting and usage decision process, packaging and accountability of the study vaccines.

7.3. Dosage and administration of study vaccines

Table 15 Dosage and administration

Type of contact and timepoint	Volume to be administered	Study group	Treatment name	Route ¹	Site	Side ³
Visit 1 (Day 0) Visit 5 (Day 30)	0.5 ml	RSV-Ld	ChAd155 5x10 ⁹ vp	IM	Deltoid ²	Left
	0.5 ml	Placebo-Ld	Placebo 0.5	IM	Deltoid ²	Left
	0.15 ml	RSV-Md	ChAd155 1.5x10 ¹⁰ vp	IM	Deltoid ²	Left
	0.15 ml	Placebo-Md	Placebo 0.15	IM	Deltoid ²	Left
	0.5 ml	RSV-Hd	ChAd155 5x10 ¹⁰ vp	IM	Deltoid ²	Left
	0.5 ml	Placebo-Hd	Placebo 0.5	IM	Deltoid ²	Left

¹IM: Intramuscular.

²If the muscle size is adequate; otherwise injections might be done in the anterolateral thigh. The site of administration of Dose 2 should preferably remain the same as the site of administration of Dose 1.

³Preferable side for administration.

RSV-Ld: low dose ChAd155-RSV vaccine (5 x 10⁹ vp); **RSV-Md:** middle dose ChAd155-RSV vaccine (1.5 x 10¹⁰ vp); **RSV-Hd:** high dose ChAd155-RSV vaccine (5 x 10¹⁰ vp).

Note that ChAd155-RSV vaccine middle dose will be given as a 0.15-mL fractional dose of the high dose (0.5 mL). Refer to the SPM for detailed instructions on study vaccine administration.

Minimizing environmental contamination with genetically modified organisms

Each product will be used in accordance with the applicable genetically modified organism regulations.

To minimize release of the recombinant vectored vaccine virus into the environment, each vaccine is produced under good manufacturing practice conditions with the handling of live material in appropriate laboratory facilities. This is to ensure that any release of modified organism is contained, inactivated and incinerated, using single use equipment as much as possible, to avoid release of modified genetic material into the environment.

After each vaccination, the injection site will be covered with a dressing in order to absorb any virus that may leak out through the needle track. The dressing will be removed only after 30 minutes and will be disposed as genetically modified organism waste by autoclaving or in accordance with the applicable guidelines/SOPs at the investigator's site.

7.4. Replacement of unusable vaccine doses

In addition to the vaccine doses provided for the planned number of subjects (including over-randomization when applicable), at least 10% additional vaccine doses will be supplied to replace those that are unusable.

The investigator will use SBIR to obtain the replacement vial number. The replacement numbers will be allocated by dose. The system will ensure, in a blinded manner, that the replacement vial matches the formulation the subject was assigned to by randomization.

7.5. Contraindications to subsequent vaccination

The following events constitute absolute contraindications to further administration of ChAd155-RSV vaccine. If any of these events occur during the study, the subject must not receive additional doses of vaccine but may continue other study procedures at the discretion of the investigator (see Section 9.5).

- Anaphylaxis following the administration of vaccine.
- Any confirmed or suspected immunosuppressive or immunodeficient condition, including HIV infection.
- Any condition that in the judgment of the investigator would make IM injection unsafe.
- Current autoimmune disease.
- Acute or chronic, clinically significant pulmonary, cardiovascular, hepatic or renal functional abnormality, as determined by physical examination or laboratory tests.
- Failure to thrive.

The following events constitute contraindications to administration of ChAd155-RSV vaccine at that point in time; if any of these events occur at the time scheduled for vaccination, the subject may be vaccinated at a later date, within the time window specified in the protocol (see Section 6.5), or the subject may be withdrawn at the discretion of the investigator (see Section 9.5).

- Acute disease and/or fever at the time of vaccination.
 - Fever is defined as temperature $\geq 37.5^{\circ}\text{C}/99.5^{\circ}\text{F}$ for oral, axillary or tympanic route, or $\geq 38.0^{\circ}\text{C}/100.4^{\circ}\text{F}$ for rectal route. The preferred route for recording temperature in this study will be axillary.
 - Subjects with a minor illness (such as mild diarrhea, mild upper respiratory tract infections) without fever can be administered all vaccines.
- Any Grade 1 abnormality with potential clinical relevance or any \geq Grade 2 abnormality in hematological parameters detected in the Day 7 blood sample (refer to Section 6.6.11.2, Figure 2 and Appendix C).

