testing will be performed on that day. Further testing may be required to investigate a finding or guide subject management based on the investigators clinical judgment. Subjects' parent(s)/LAR(s) will be instructed to contact the investigator/study staff if their child presents symptoms of spontaneous bleeding or easy bruising or if their child develops a rash in the month following vaccination, in order to detect any thrombocytopenic petechiae or purpura. The investigator will, based on his/her medical judgement, appropriately investigate infants with clinical suspicion of low platelets.

- Refer to Section 6.6.11.2 and Figure 2 for information about the re-testing of samples in case of any Grade 1 abnormality with potential clinical relevance or any \geq Grade 2 abnormality.
- Blood sample for **RSV serostatus** will be taken from all infants at Screening.
- Blood samples for **CMI** are limited to those in investigational sites with a laboratory in proximity capable to perform WBS necessary for the CMI assay. In those sites, samples will be taken from all subjects at Screening and on Day 30, Day 60, and Day 365.

Note: Blood samples for CMI taken on Day 7 and Day 37 for subjects enrolled under protocol amendment 1 will still be assessed for CMI.

- Blood samples for **humoral immunogenicity** will be taken from all subjects at Screening and on Day 30, Day 60, and Day 365.
 - Blood sample for **assessment of mechanism of illness (potential ERD)** will be taken from subjects hospitalized for LRTI (only for RSV-positive subjects using a locally available RSV test).
 - Nasal swab: there will be monthly nasal swab to detect asymptomatic RSV infections during the RSV season and if following active or a passive surveillance contacts, a subject presents symptoms of RTI, a nasal swab will be collected.

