^e At Screening, for infants with hematological/biochemical values out of normal range which are expected to be temporary, a re-screening visit may be scheduled during which blood sample collection for hematology/biochemistry will be repeated (maximum one re-screening visit per infant is allowed; blood for CMI response and humoral response will not be re-sampled at the re-screening visit, if already done before).

^f If any Grade 1 abnormality with potential clinical relevance (according to investigators judgment) or any ≥ Grade 2 abnormality is detected, or for further evaluation of clinical suspicion of low platelet count, refer to Section 6.6.11.2 and Figure 2 for re-test.

^g Blood samples to be taken before vaccination.

^h If during passive or active surveillance contact, the investigator/study staff assesses that an infant presents a potential RSV-RTI (refer to Table 4 for definition), the potential RSV infection will be assessed by quantitative RT-PCR.

ⁱ Only when the unscheduled visit occurs within the AE reporting time frame, i.e. from Day 0 to Day 6 for solicited AEs and from Day 0 to Day 29 for unsolicited AEs.

^j Signs and symptoms to be recorded in the eCRF are listed in the SPM.

^k Subject's parent(s)/LAR(s) will be instructed to record on the RTI episode card the start date and the end date of the following symptoms (cough, runny nose, blocked nose, difficulty in breathing, or wheezing) and to return it to the investigator at the next visit or by mail (e-mail or postal mail).

^l Blood sample collected for subjects hospitalized for LRTI (only for RSV-positive subjects using a locally available RSV test); Refer to Section 6.7.3.

^m Nasal swab collected at the monthly surveillance for asymptomatic RSV-RTI will be tested by quantitative RT-PCR.

ⁿ For RSV testing and respiratory viral panel (RVP) at a local routine laboratory, where available.

^o In investigational sites with a laboratory in proximity capable to perform WBS necessary for the CMI assay.

^p Day 7 hematology testing will be performed if any ≥ Grade 1 for platelet decrease is detected on Day 1 after vaccination. Similarly, hematology testing on Day 37 will be performed if any ≥ Grade 1 for platelet decrease is detected on Day 31.

CONFIDENTIAL

204838 (RSV PED-002)

Protocol Amendment 4 Final

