6.6.11.2. Blood sampling for hematology and biochemistry

- A volume of maximum 1.2 mL of whole blood should be drawn from all infants for analysis of the hematology parameters (refer to [Table 11](#)) at each pre-defined timepoint.
- A volume of maximum 1.1 mL of whole blood should be drawn from all infants for analysis of the biochemistry parameters (refer to [Table 11](#)) at each pre-defined timepoint.

Hematology and biochemistry parameters assessment will be performed according to laboratory practices.

[figure not shown]
Day 7 hematology testing will be performed if any \geq Grade 1 for platelet decrease is detected on Day 1. Similarly, hematology testing on Day 37 will be performed if any \geq Grade 1 for platelet decrease is detected on Day 31 (refer to [Figure 2](#) and [Appendix C](#)).

If any Grade 1 abnormality with potential clinical relevance (according to investigators judgment, refer to the [glossary of terms](#)) or any \geq Grade 2 abnormality is detected (refer to [Figure 2](#) and [Appendix C](#)):

- at **Screening**, for infants with hematological/biochemical values out of normal range which are expected to be temporary, a re-screening visit may be scheduled during which blood sample collection for hematology/biochemistry will be repeated (maximum one re-screening visit per infant is allowed within the interval planned in [Table 6](#)).
- at **Day 7**, the relevant hematology/biochemistry parameter(s) **must** be re-tested before administration of vaccine Dose 2, either during an unscheduled visit or at the Dose 2 vaccination visit itself (provided results are obtained before vaccination). Only if the concerned parameter(s) is/are within the acceptable range (i.e. within normal range or Grade 1 without clinical relevance), vaccine Dose 2 can be administered. If the concerned parameter(s) is/are not within the acceptable range within the allowed interval for the second dosing visit, Visit 5, the infant will not receive Dose 2 but should still continue the study for safety follow-up (up to Day 730).
- at **Days 30, 37 and 60** the relevant hematology/biochemistry parameter(s) **may** be re-tested as per the opinion of the investigator.

Note: For safety reasons and specifically for further investigation of an AE of specific interest (suspected bleeding or low platelet count), blood can be re-sampled for hematology and biochemistry assessment.

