Figure 2 Schematic overview of required additional hematology and biochemistry testing during the study

Note: For safety reasons and specifically for further investigation of an AE of specific interest (suspected bleeding or low platelet count), blood can be re-sampled for hematology and biochemistry assessment.

6.6.11.3. Nasal swab and other specimen for local assay**Nasal swab and other specimen for local assay collected during assessment visit**

If during passive or active surveillance contact, the investigator/study staff assesses that an infant presents a potential RSV-RTI (refer to 9.2), a nasal swab and another specimen for local assay will be collected during an assessment visit:

- The nasal swab will allow assessing the potential RSV infection by quantitative RT-PCR at sponsor laboratory.
- The specimen for local assay will allow assessing the potential RSV infection and RVP at a local routine laboratory, where available. The specimen type will depend on the assay run locally.

Nasal swab collected to detect asymptomatic RSV infections

During RSV season, there will be monthly nasal swabs to detect asymptomatic RSV infections. These nasal swabs will allow assessing the potential RSV infection by quantitative RT-PCR at sponsor laboratory.

Refer to the SPM for more details about nasal swab.

6.6.12. Detection of spontaneous bleeding or easy bruising and evidence of bruising or petechiae

Subjects' parent(s)/LAR(s) will be instructed to contact the investigator/study staff if their child presents symptoms of spontaneous bleeding or easy bruising or if their child develops a rash in the month following vaccination, in order to detect any thrombocytopenic petechiae or purpura. Refer to Sections 9.1.5 and 9.4.3 for reporting of adverse events of specific interest (spontaneous or excessive bleeding).

At Visit 2 (Day 1), Visit 3 (Day 3)*, Visit 4 (Day 7), Visit 6 (Day 31), Visit 7 (Day 33)*, and Visit 8 (Day 37), the investigator will perform a clinical examination with special attention given to detection of spontaneous bleeding or easy bruising and evidence of bruising or petechiae. Episodes of spontaneous bleeding or easy bruising and evidence of bruising or petechiae will be recorded in the eCRF.

* The visits on Day 3 and Day 33 may be replaced by a phone call by the investigator/study staff to inquire of the infants' general health and to solicit reports of a rash, spontaneous bleeding or easy bruising.

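### The only infant-level graded laboratory bar to Dose 2 in the visible text reads a Day 7 sample triggered by platelets alone, so a Grade 2-4 haemoglobin or white-cell result on Day 1 with normal platelets meets no graded bar

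*Protocol*

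**What the plan says.** **The bar.** Protocol 7.5 lists temporary contraindications to Dose 2. The one graded laboratory item covers a Grade 1 finding of potential clinical relevance, or any Grade 2 or worse "abnormality in hematological parameters detected in the Day 7 blood sample".

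**The matching procedure.** In 6.6.11.2, under the Day 7 bullet, an affected parameter must be "re-tested before administration of vaccine Dose 2, either during an unscheduled visit or at the Dose 2 vaccination visit itself", in the latter case "provided results are obtained before vaccination". Dose 2 is allowed only if the parameter is back in the acceptable range, and is not given if that does not happen within the Visit 5 window. For Days 30, 37 and 60, an abnormal parameter may "be re-tested as per the opinion of the investigator". There is no Day 1 bullet.

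**The trigger.** Sections 3 and 6.6.11.2 and Table 11 make Day 7 haematology conditional on a Grade 1 or worse platelet decrease on Day 1. Day 1 and Day 30 haematology is taken from every infant.

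**The pointers.** Table 5 footnote f, attached to the Day 1 haematology cell, covers a clinically relevant Grade 1 or any Grade 2 or worse result, "or for further evaluation of clinical suspicion of low platelet count, refer to Section 6.6.11.2 and Figure 2 for re-test". Section 3 likewise sends the reader to 6.6.11.2 and Figure 2 "for information about the re-testing of samples in case of any Grade 1 abnormality with potential clinical relevance" or any Grade 2 or worse. Figure 2 is titled "Schematic overview of required additional hematology and biochemistry testing during the study"; its content is not visible. For the Day 30 draw, footnote g says only "Blood samples to be taken before vaccination".

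**The concern.** The bar in 7.5 is worded for haematological parameters in general, but an infant comes under it only through platelets. Two infants with the same Day 1 haemoglobin or white-cell abnormality can therefore be handled under different written rules because of an unrelated platelet value.

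The plan itself treats these parameters as relevant to safety. Section 5.3 excludes the same grades before Dose 1. Table 11 requires the differential to be recorded, and Table 25 grades neutrophils and lymphocytes. Section 11.4 names haemoglobin and neutrophils as examples of concerns that may lead the IDMC to continue enrolling at the lower dose. At stake is whether a first-in-infant study applies its own Dose 2 criterion to a graded result it already holds.

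**Working it through.** **1. Follow two infants through the written rules.** Both have Day 1 haemoglobin of 8.5 g/dL, which is Grade 2 in Table 25 (8.0 to <9.0).

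| | Infant A | Infant B |
|---|---|---|
| Day 1 platelets (/mm³) | 149,000 (Grade 1: 75,000 to <150,000) | 150,000 (no grade) |
| Day 7 haematology | drawn | not drawn |
| If haemoglobin stays Grade 2 | re-test mandatory; must be in range before Dose 2 | no graded bar in 7.5; no Day 1 bullet in 6.6.11.2 |

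The same holds for leukocytes, neutrophils and lymphocytes: four of the five graded haematology parameters reach the rule only through the fifth.

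**2. Does the Day 30 draw close the gap?** Not in the written text. Footnote g requires blood to be taken before Dose 2, not the result to be known, whereas the Day 7 bullet does require the result. Re-testing at Day 30 is optional.

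**3. Do the holding rules close it?** Rule 2c needs Grade 3 or worse, not attributable to another cause, in at least 25% and at least 2 infants of a vaccine group. With 16 per group that is 4 infants.
- P(X ≥ 4), X ~ Bin(16, 0.10) = 6.8%, so 93.2% not met. The plan states more than 90%.
- P(X ≥ 4) = 59.5% at a 25% rate and 63.0% at 26%. The plan states more than 60% above 25%.

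The plan's figures reproduce. With 8 per group the threshold is 2 infants: P(met) = 18.7% at 10% and 63.3% at 25%. A single infant never meets rule 2c, and Grade 2 never counts. Rule 1d needs bleeding together with platelets below 50,000/mm³. Neither is an infant-level haemoglobin or white-cell criterion.

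**4. How many infants?** The documents give no rate for a Day 1 Grade 2 or worse non-platelet result. The rates below are assumptions, applied to the 32-48 vaccinees in Protocol 1.3. Expected number = n × p; P(at least one) = 1 − (1 − p)^n.

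| Assumed p | Expected, n = 32 / 48 | P(at least one), n = 32 / 48 |
|---|---|---|
| 0.5% | 0.16 / 0.24 | 14.8% / 21.4% |
| 1% | 0.32 / 0.48 | 27.5% / 38.3% |
| 3% | 0.96 / 1.44 | 62.3% / 76.8% |

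**5. Is a re-test feasible?** Table 6 puts Dose 2 at 23-36 days after Dose 1. From the Day 1 sample that leaves 23 − 1 = 22 to 36 − 1 = 35 days.

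Blood volume, from Table 7: 7.8 + 1.2 + 1.2 + 6.8 + 1.2 + 1.2 + 6.8 = 26.2 mL, the plan's maximum, which counts the Day 7 and Day 37 draws. An infant with normal Day 1 platelets has no Day 7 draw, so one re-test gives 26.2 − 1.2 + 1.2 = 26.2 mL, or 25.0 mL if Day 37 is also not drawn. The eight-week limit in 1.2.4.3 is 54.7 mL.

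**The case against.** **Figure 2 may hold the missing rule.** Section 7.5 itself refers to Figure 2, footnote f sends the Day 1 result there, and its title speaks of required testing. This stands for the re-test: one is evidently intended. It does not stand for the bar, because 7.5 still names only the Day 7 sample.

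**Infants are not unprotected.** Section 6.6.10 reschedules vaccination if the infant's health on the day precludes it. Unscheduled visits exist for out-of-range values. Section 7.5 has ungraded contraindications, including suspected immunodeficiency, which could catch severe neutropenia or lymphopenia. Blood dyscrasias are a named example of a serious event in 9.1.2, and SAEs within 30 days of vaccination reach the iSRC and IDMC within 48 hours. The iSRC sees unblinded haematology about every three weeks, so a Day 1 result would ordinarily be reviewed before Dose 2. All of this stands. These safeguards rest on judgment or act on the study as a whole; none is a graded Dose 2 criterion for the individual infant.

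**The conditional draw was deliberate.** The Amendment 2 rationale in Appendix D gives family burden first, then continued oversight of thrombocytopenia, the timing of the platelet nadir, and agreement by the IDMC and the sponsor. It would be wrong to say that the nadir was the only reason. The rationale supports sampling less often. It gives no visible reason for leaving the other graded parameters outside the bar.

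**Low frequency.** This also stands. Grade 2 or worse is excluded at screening, the adult study showed no haematology signal, and the haemoglobin drop seen with another vector was mild. The 62-77% in the table comes only from the assumed 3%.

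**Conclusion.** The point holds for the visible text: a Grade 2-4 haemoglobin, leukocyte, neutrophil or lymphocyte result on Day 1 with normal platelets meets no graded bar to Dose 2. Its size is unknown and probably small: across assumed rates of 0.5-3%, 0.16 to 1.44 vaccinees. It is a should-fix because the study already has the rule and leaves part of its own graded data outside it.

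A reader might infer that such an infant would get no re-test, or would simply be vaccinated. The documents do not support that: Figure 2 is unseen, footnote f points to a re-test, and an investigator can withhold the dose. A reader might also infer that the bar was knowingly dropped for the other parameters; the text shows only that no reason is given.

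Confidence is medium, because Figure 2 could narrow the gap.

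**What to change.** In 7.5 and 6.6.11.2, apply the existing rule to any haematology result available from the Day 1, conditional Day 7 or unscheduled samples after Dose 1. A clinically relevant Grade 1, or any Grade 2 or worse, must be re-tested, and the affected parameter known to be in the acceptable range before Dose 2. The re-test can be at an unscheduled visit, or from the Day 30 draw if resulted before dosing. For platelets, the conditional Day 7 sample counts as the re-test. Align footnote f and Figure 2 with this wording.

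**Cost.** Protocol text and one figure, no new routine draw, and an occasional 1.2 mL re-test within the 26.2 mL maximum. Under blinding the rule falls on all 64-96 infants, placebo included; at an assumed 1% in both arms that is 64 × 0.01 = 0.64 to 96 × 0.01 = 0.96 infants. Some may have Dose 2 delayed within the 23-36 day window or missed. An infant who misses Dose 2 leaves the immunogenicity per-protocol set (SAP 5.1.2 and 9) and does not count toward the 16 two-dose infants the IDMC must review per step before escalation. Withdrawals are not replaced (Protocol 10.2).

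The change will not make practice fully uniform across sites, because the relevance of a Grade 1 result stays with the investigator.
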